#### **14.0** Potential Benefits to Participants

14.1 Potential Benefits: It is possible that a participant may have an improvement in depressive symptoms from this treatment but there are no anticipated direct benefits to participation in this research project. The contribution to general knowledge on the research topic may be a societal benefit.

#### **15.0** Statistical Considerations

15.1 Data Analysis Plan:

Effectiveness analyses: Repeated measures ANOVAs will examine the effect of condition (active tDCS + MBT and sham tDCS + MBT) on pre- and postintervention MADRS scores, rumination scores, mindfulness scores, and emotion regulation scores. EEG outcomes will include alpha asymmetry, LPP amplitude, coherence, and entropy at rest, during rumination, during mindfulness, and during emotion processing. ECG outcomes will include heartrate variability. MRI outcomes will include DLPFC-DMN, DLPFC-limbic system, and within-DMN RSFC, as well as DLPFC, limbic, and DMN activation to rumination and emotional processing tasks. Additional analyses will be conducted to assess whether changes in emotion regulation, mindfulness, and rumination moderate changes in depression symptoms. Regression analyses will be run on baseline measures to identify predictive biomarkers of MBT/tDCS treatment response. Correlation analyses will be conducted between the degree of change in clinical scores (depression symptoms, rumination, emotion regulation) with degree of change in neuroimaging and mindfulness indices.

Neuroimaging data analysis: We will optimize components from the HCP minimum processing pipeline to fit our imaging protocols and will include gradient non-linearity distortion corrections, distortion correction caused by magnetic field inhomogeneity, co-registration of functional and anatomical images, non-linear registration to MNI template brain, intensity bias corrections, highpass filtering, re-sampling of the data onto the cortical mesh (surface analyses), and denoising of the data using ICA-fix (Griffanti et al., 2014). Network Analysis. We will quantify RSFC within fronto-limbic and default mode networks as described in our prior work.

EEG: *Change in alpha band asymmetry*: Eyes-open and eyes-closed restingstate EEG alpha power (8-13 Hz) will be calculated for left and right prefrontal electrodes using a fast-fourier transform approach. We will define the alpha asymmetry index (AAI) as the ratio of the left prefrontal alpha power to the right prefrontal alpha power. A similar AAI analysis will be carried out for the rumination EEG data. *Coherence Analysis*: We will investigate resting-state EEG correlates of DMN functional connectivity by computing the coherence between posterior and prefrontal cortical regions. In order to specifically assess alpha and beta band coherence changes within the DMN, we will choose channel Pz to represent the precuneus/posterior cingulate and channel Fz to represent the medial prefrontal cortex/anterior cingulate. We will further assess changes in coherence between the DMN (channels Fz, Pz) and the DLPFC (channels F3, F4). *P300 Amplitude*. P300 ERP responses will be measured during the
Go/No-Go and Flanker tasks and will be compared across different types of trials (e.g., go versus no-go trials and congruent versus incongruent trials). *ERN Amplitude*. Error Related Negativity (ERN) ERP responses will be measured during the Go/No-Go and Flanker tasks and will be compared across different types of trials (e.g., trials after correct versus incorrect responses).

ECG: Estimates of HRV will be calculated based on recommendations by an international committee (Malik et al., 1996). Power spectral analyses will be used to estimate contributions from sympathetic (low frequency) and parasympathetic (high frequency) components.

Number of study visits completed may be used as a covariate in analyses.

15.2 Power Analysis:

Since we do not have pilot data with adolescents using either of these interventions, we were unable to conduct a power analysis to calculate an appropriate sample size. Budget and time constraints necessitate a relatively small sample size. While some studies in the literature have reported significant effects using similarly small samples, we cannot be certain that the study is powered appropriately to confirm or refute our hypotheses. Therefore, we have framed the project with a primary goal of establishing feasibility (our ability to recruit, adolescents' acceptance of randomization, adolescents' tolerability of the interventions) and of collecting data that will allow a power calculation to determine the sample size necessary for the federal grant to follow this work.

15.3 Statistical Analysis: A p-value of .05 will be used to determine significance for behavioral measures and a p-value of .005 will be used to determine significance for neuroimaging measures. Paired t-tests will be used to compare baseline versus post-tDCS and post-MBT intervention for both intervention groups for biological, clinical, and behavioral measures. Between-group t-tests will be conducted on the side-effects to examine group differences in prevalence of side effects. Feasibility will be determined by looking at descriptive statistics about enrollment and eligibility of people that express interest in the study and enroll as well as retention of enrolled participants. Correlation analysis will be conducted to assess how changes in clinical and behavioral relate to biological measures following intervention. Mixed repeated measures ANOVAs will test our hypothesis that the active tDCS group will show greater change than the sham tDCS group with condition (active or sham) as the between participant measures; within-participant measures will include behavioral.

clinical, and biological indices. Regression models will also be conducted on baseline measures (e.g., RSFC, task activation, trait mindfulness and emotion regulation) to assess biomarkers of treatment response. Behavioral indices include performance on the GoGreen, Middle Fish, and CRT. Biological indices include EEG (e.g., AAI, coherence, entropy at rest and during mindful breathing, as well as LPP amplitude during the Emotion Regulation Task, P300 and ERN during the GoGreen and Middle Fish tasks), ECG data (HRV), and MRI data (e.g., DMN, DLPFC, and Limbic activation to Hariri and Rumination Tasks and functional connectivity at rest and during mindful breathing). Clinical measures include depression symptoms, rumination scores, and mindfulness scores.

15.4 Data Integrity: Outlier analyses will be conducted and data values that exceed three standard deviations will be removed or winsorized.Neuroimaging data will also be examined for excessive motion. Data will be checked by [name].

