#### 4.0 Study Intervention(s)/Investigational Agent(s)

4.1 Description:

Mindful Breathing Training (MBT): All participants will undergo mindful breathing training (MBT). MBT is a mindfulness-based intervention that guides participants to pay attention to the present experience. Participants will be trained to become aware of mind-wandering, disengage, and shift attention back to the present experience. Participants will practice mindful breathing using a computerized application that they will be able to access on the web. This training will be administered through a University of Minnesota server on an internet browser (e.g., Google Chrome). During this task, participants will close their eyes and focus on their breath, tapping at the end of each breath. Participants will first complete five sessions (for 10, 12.5, 15, 17.5, and 20 minutes) of mindful breathing training at home using a personal laptop, tablet, or cell phone over five days. Following this training, participants will be randomized to undergo either ten 20-minute sessions of active or sham tDCS concurrent with MBT across two weeks in lab. Participants are not required to complete all five mindful breathing sessions prior to starting in-person treatment. Following lab MBT training with either active or sham tDCS, participants will complete 15 sessions of MBT training across three weeks at home or inperson.

**tDCS**: We will use transcranial direct current stimulation (tDCS), a noninvasive brain stimulation technique that can modulate brain activity and connectivity, to stimulate the dorsolateral prefrontal cortex (DLPFC). Weak electrical current (~2mA) is applied to the scalp using anodal and cathodal

electrode sponges, which increase or decrease cortical excitability respectively. Research has shown in both healthy participants and patients (e.g. Alzheimer's disease, Parkinson's disease, and depression) that tDCS has the potential to modulate synaptic strengthening and neurotransmitter-dependent plasticity underlying changes in behavior and learning (Lang et al., 2005). Sham stimulation will serve as a control condition with current applied only for the first and last 30 seconds of the 20-minute session.

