#### • Mindful Breathing Training Description

30 sessions of MBT: Participants will be instructed to practice mindfulness and will complete a guided computerized task. During the computerized task, they will be asked to focus on the sensations of their breaths. They will tap at the end of each breath and receive feedback. Participants will be trained to use the mindful breathing program after their last in-person baseline visit. Training will involve a brief overview of mindful breathing and a one-minute training to introduce the task. The first 5 sessions will be competed at home for 10, 12.5, 15, 17.5, and 20 minutes respectively. The first session may be completed in person during the mindful breathing training to ensure participants understand how to use the training program. Participants are not required to complete all five breathing sessions prior to starting in-person treatment. The next 10 sessions will last 22 minutes and will be done concurrent with active or sham tDCS. The remaining 15 sessions will last 20 minutes and participants will be given the option of completing these either in-person (only if the study team determines that it would be helpful for the participant to complete these sessions in-person) or at home using a personal laptop, tablet, or cell phone. This app will collect data about the quality of focus during MBT and session completion information. See Figure 1.

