#### • EEG

We will obtain EEG to quantify band power, alpha asymmetry, entropy, coherence, the late positive potential, and phase-amplitude coupling. EEG data will be collected at baseline, within 1-2 business days following the tDCS intervention, and within 1-2 business days following the 3-weeks of MBT training at home/in-person. Lab staff will place a 32-channel EEG cap on each of the participants for a baseline and post-intervention EEG

(done at the beginning of treatment session 1 and the end of treatment session 10). The leads will be positioned to optimally obtain frontal and midline regions. All participants will undergo 2 3-minute rest EEG scans with their eyes open and closed. Participants will also be asked to describe a negative and neutral thought they have and fixate on this thought for 3 minutes each. Participants will also be asked to practice mindful breathing for 10-minutes at the post-intervention EEG.

- Flanker task assesses interference processing. Participants are asked to indicate the direction of a central arrow that is flanked by two arrows on each side that are either pointing in the same direction (congruent) or the opposite direction (incongruent) as the central arrow (Albrecht et al., 2008). This will be administered using Eprime.
- Go/no-go task assesses attention and inhibition.
   Participants see letters and are asked not to respond to one letter and respond to all other letters (Wodka et al., 2007). This will be administered using Eprime.
- If the EEG data collected is not of high enough quality (e.g., due to excessive motion) or if EEG data is not acquired due to technical difficulties, the participant may be invited to repeat the EEG scan and will be compensated for the repeated EEG scan.

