#### • Electrocardiographic (ECG)

 ECG data will be collected to quantify heart rate variability (HRV). ECG data will be collected concurrent with EEG data collection under rest (6 minutes), under rumination and neutral thinking conditions, and mindful breathing conditions (10 minutes). ECG data will be collected during the EEG sessions at baseline, within 1-2 business days following the tDCS intervention, and within 1-2 business days following the 3-weeks of MBT training at home/inperson.

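### Section 15.1 reads low-frequency HRV power as sympathetic and high-frequency power as parasympathetic at any breathing rate; for recordings below the band edge that reading can point the wrong way

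*Combined protocol and SAP*

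**What the plan says.** The ECG paragraph of Section 15.1 has two sentences. The first defers to an outside standard: "Estimates of HRV will be calculated based on recommendations by an international committee". The second fixes the interpretation: "Power spectral analyses will be used to estimate contributions from sympathetic (low frequency) and parasympathetic (high frequency) components". Neither gives band limits in Hz or mentions respiration. The only covariate named in 15.1 is the number of visits completed.

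Section 5.2 (Electrocardiographic) sets the recording conditions: "ECG data will be collected concurrent with EEG data collection under rest (6 minutes), under rumination and neutral thinking conditions, and mindful breathing conditions". The schedule of activities places the mindful-breathing recording at EEG 2 and 3 only, and the EEG part of Section 5.2 agrees: "Participants will also be asked to practice mindful breathing for 10-minutes at the post-intervention EEG".

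Section 4.1 describes the training task: "During this task, participants will close their eyes and focus on their breath, tapping at the end of each breath". No pace is set and nobody is told to slow down. Both arms receive the training.

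HRV is an ECG outcome in 15.1 and a biological index in 15.3. It is not named in the aims (Section 1.2) or among the endpoints (Section 3.0).

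**The concern.** Reading high-frequency power as parasympathetic rests on heart rate rising and falling with each breath, an effect taken here, as a working assumption, to be mainly vagal. That variation lies at the breathing frequency, wherever that is. A fixed band captures it only while breathing is faster than the band's lower edge. Below the edge the same vagal power lands in the low-frequency band, and the plan's rule labels it sympathetic.

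The trial teaches attention to the breath and records ECG while participants practise it. If some of them breathe below the edge, an unchanged vagal state would be read as a parasympathetic fall with a sympathetic rise. The plan records nothing that would show which recordings are affected.

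**Working it through.** **No figure to reproduce.** The plan gives no band limits, breathing rate, HRV effect size or power calculation. The check is a unit conversion followed by an illustrative simulation on assumed inputs.

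**Step 1: the threshold.** Breaths per minute = 60 × edge in Hz.
- 0.12 Hz × 60 = 7.2/min
- 0.15 Hz × 60 = 9/min
- 0.20 Hz × 60 = 12/min

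**Step 2: the shift in power.** Assumptions: low-frequency band (LF) 0.04–0.15 Hz and high-frequency band (HF) 0.15–0.40 Hz; a respiratory sinusoid of amplitude 40 ms (power 40²/2 = 800 ms²) with 5% breath-to-breath jitter; a non-respiratory LF component of SD 20 ms (20² = 400 ms²); Welch spectrum; 100 replicates of 600 s, the length of the mindful-breathing recording. Both components stay constant and only breathing rate changes.

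| Breaths/min | Hz | LF (ms²) | HF (ms²) | LF/HF |
|---|---|---|---|---|
| 15 | 0.250 | 379 | 799 | 0.47 |
| 12 | 0.200 | 381 | 796 | 0.48 |
| 10 | 0.167 | 399 | 780 | 0.51 |
| 9 | 0.150 | 924 | 258 | 3.6 |
| 8 | 0.133 | 1172 | 9 | about 127 |
| 6 | 0.100 | 1165 | about 0 | not meaningful |

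- From 15 to 6/min, LF rises by 1165/379 = 3.1-fold and HF vanishes.
- From 15 to 10/min, LF's share of LF + HF goes from 379/1178 = 32% to 399/1179 = 34%.
- With 180 s records, the length of the rumination and neutral conditions, the pattern is the same: LF/HF is 386/799 at 15/min and 1175/9 at 8/min.
- With respiratory amplitude 20 ms, the LF rise from 15 to 6/min is 568/380 = 1.5-fold. With 60 ms it is 2196/376 = 5.8-fold.

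A second simulation, with non-respiratory LF power of 500 ms² and a different jitter model, gives LF/HF of 491/824 = 0.6 at 15/min and 1256/63 = 20 at 8/min. Direction and threshold agree. The ratio below the edge (20 against 127) depends on jitter and spectral leakage and should not be relied on.

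**Step 3: which comparisons are exposed.**
- *Mindful breathing against rest at EEG 2 or 3:* the most direct exposure, because the two conditions may differ in breathing rate.
- *Baseline to post at rest (paired tests, Section 15.3):* exposed only if resting breathing also falls below the edge. Mindful breathing has no baseline recording and so no baseline-to-post test of its own.
- *Active against sham:* exposed only if breathing rate differs by arm.
- *Correlations of clinical with biological change:* exposed on the same condition as the HRV change they use.

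**The case against.** The strongest reply is that nothing in the documents shows anyone breathing below the edge. Participants attend to their breath and tap; they are not paced or told to slow. A reader might infer that any calming of the breath will be reported as sympathetic activation. The documents do not support that, and the table shows that slowing within the range above the edge does no material harm.

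A reader might also infer that thirty training sessions will have slowed resting breathing by the post-tDCS visit. At most 5 + 10 = 15 sessions precede EEG 2, the five home sessions need not all be completed first, and no resting breathing rate is given at any visit. Nor does the plan imply a biased randomised contrast, since both arms train alike.

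Three further points stand. The cited committee standard may carry its own bands and a respiration caveat, so the absence of a safeguard can be asserted only of the plan's own text. Section 15.3 lists HRV without naming a condition, so a mindful-breathing-against-rest test is a natural use of the data but not a specified one. No direction is predicted for HRV, so a reversed reading would contradict no stated hypothesis.

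The interpretive sentence remains. It is unconditional, it covers recordings made during breath practice, and nothing planned would reveal a recording to which it does not apply.

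**Conclusion.** The point holds conditionally. For any recording with breathing below the band edge, the rule in 15.1 counts vagal respiratory power as sympathetic and can reverse the direction of the HRV reading; above the edge there is no material error. The threshold is 9 breaths/min if the edge is 0.15 Hz, and 7.2 to 12 for edges of 0.12 to 0.20 Hz. In the model, LF rises 1.5- to 5.8-fold between 15 and 6/min with no autonomic change. These sizes rest on assumed bands and amplitudes, and constant vagal power is imposed; they show direction and threshold and do not forecast this trial's result.

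How many recordings would be affected cannot be known from the documents, and it may be none. The consequence is confined to a mechanistic measure in a pilot of about 15 per group. The wording should still be corrected, because the possible error is one of sign and the remedy is cheap.

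**What to change.** Replace the interpretive sentence in the ECG paragraph of Section 15.1 with three provisions:

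- **Labels.** Report LF power and LF/HF descriptively and do not interpret them as sympathetic activity.
- **Breathing rate.** Derive it from the ECG and report it by arm, visit and condition. Section 5.2 says of the training program: "They will tap at the end of each breath and receive feedback". A reader might take the taps to be a ready-made respiration record. However, the same section lists the stored data as focus quality and session completion, and the EEG description does not mention tapping. Use taps only if they are confirmed to be time-stamped and recorded during the EEG session.
- **Bands.** State the limits in Hz. Where the respiratory peak lies below the HF edge, do not read fixed-band HF power as the vagal index. As a sensitivity analysis, report RMSSD or power in a band centred on the breathing frequency. RMSSD needs no band edge, but for a sinusoid of amplitude A and frequency f, sampled at mean beat interval T, it equals √2·A·|sin(πfT)|. It therefore also shrinks as breathing slows, so it should be read beside the breathing rate.

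The cost is a wording change and modest extra processing of ECG already planned, with no new sensor. The trial gives up a claimed sympathetic index, and ECG-derived respiration is noisier than a respiration belt.

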#### 1.0 Objectives

1.1 Purpose: This study will investigate whether transcranial direct current stimulation (tDCS) targeting the dorsolateral prefrontal cortex (DLPFC) can enhance the therapeutic effect of mindful breathing training (MBT) for adolescent depression. The objective is to enhance connectivity between the DLPFC with the amygdala and Default Mode Network (DMN) circuits as well as to enhance emotion regulation abilities and decrease rumination to reduce symptoms of depression. This will aid in the development of novel treatments for depression.

*1.2* This study will investigate the following aims:

**Aim 1**: To demonstrate the feasibility of recruiting and randomizing adolescents with depression to a research protocol involving MBT and tDCS. We expect that adolescents will be willing to enroll in a randomized trial involving MBT and tDCS.

**Aim 2**: To test the tolerability of MBT and tDCS in adolescents. We expect that MBT will be well-tolerated and that active tDCS will show no difference in tolerance compared to sham stimulation.

**Aim 3**: To examine whether tDCS can enhance the effects of MBT. We expect the MBT + tDCS group will show greater reduction in depressive symptoms compared to the MBT + sham stimulation group.

**Aim 4:** To examine the mechanisms of MBT +/- tDCS treatment. We expect that depression symptom improvement will be associated with decreased rumination, improvements in emotion regulation, increased task-based and resting state DLPFC-DMN and DLPFC-amygdala connectivity, as well as increased DLPFC activation and reduced amygdala activation during rumination and emotion processing tasks. We also expect reduced alpha asymmetry and reduced LPP amplitude during emotion regulation and emotion processing. We expect these changes will be greatest in the active tDCS + MBT group.

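### The Aim 4 correlations between change scores specify no adjustment for randomised arm, so an arm effect on both variables can distort the association they are meant to test

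*Combined protocol and SAP*

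**What the plan says.** Aim 4 (section 1.2) puts forward an association: "We expect that depression symptom improvement will be associated with decreased rumination, improvements in emotion regulation", followed by a list of connectivity, activation and EEG changes. It then adds "We expect these changes will be greatest in the active tDCS + MBT group". Aim 3 makes the matching prediction for symptoms: "We expect the MBT + tDCS group will show greater reduction in depressive symptoms compared to the MBT + sham stimulation group".

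The association is examined by correlating change scores. Section 15.1 says "Correlation analyses will be conducted between the degree of change in clinical scores (depression symptoms, rumination, emotion regulation) with degree of change in neuroimaging"; measures of mindfulness are covered too. Section 15.3 says "Correlation analysis will be conducted to assess how changes in clinical and behavioral relate to biological measures following intervention". Neither sentence mentions arm.

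Arm does appear elsewhere in section 15. The ANOVAs in 15.1 examine the effect of condition, and the mixed ANOVAs in 15.3 are specified "with condition (active or sham) as the between participant measures". The paired t-tests in 15.3 refer to both groups. The only covariate named is optional and is not arm: "Number of study visits completed may be used as a covariate in analyses".

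**The concern.** A correlation taken across both arms mixes two things: the difference between the arm means on each variable, and the association between participants inside each arm. The ANOVAs already test the first. Only the second adds information on whether participants whose biology changed more also improved more, which is what Aim 4 needs.

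If active stimulation shifts both variables, the two clusters of points move apart and produce a correlation even when there is none inside either cluster. The protocol's own hypotheses supply this condition. An association found this way could be reported as a mechanism and carried into the larger grant application that 15.2 says this study is meant to inform.

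**Working it through.** The plan gives no power, sample-size or correlation figure to reproduce, and 15.2 says no power analysis could be done. The check is therefore how far an unadjusted correlation strays when the within-arm association is known.

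**Inputs from the documents**
- About 15 per group (5.1), at least 30 completers (10.1), 1:1 allocation (5.3).
- Thresholds of .05 for behavioral and .005 for neuroimaging measures (15.3).
- Hedges' g of 0.74 for tDCS versus sham in adult depression (2.3). It is the only between-arm effect size in the documents and is background, not a design assumption.
- The MRI scan is optional (5.2), so fewer than 15 per arm may contribute.

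**Assumptions**
- Two-sided tests and normally distributed change scores.
- Equal arm effects on both variables, using 0.74 and also 0.5, 1.0 and 1.5. The last three have no source in the documents, and neither does applying 0.74 to a biological change.
- 10 per arm for an MRI subset.

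**Induced correlation.** Let d1 and d2 be the arm effects in within-arm SD units, ρ the within-arm correlation, and p = q = 0.5 the arm shares. The correlation across all participants is

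r = (ρ + pq·d1·d2) / √[(1 + pq·d1²)(1 + pq·d2²)].

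With ρ = 0 and d1 = d2 = d, this reduces to 0.25d² / (1 + 0.25d²):
- d = 0.5: 0.0625 / 1.0625 = 0.059
- d = 0.74: 0.1369 / 1.1369 = 0.120
- d = 1.0: 0.25 / 1.25 = 0.200
- d = 1.5: 0.5625 / 1.5625 = 0.360

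If either d is zero, the product is zero and so is r. Change shared by both arms, for example from the breathing training everyone receives, does not enter the formula. The sign of the induced r is the sign of d1·d2, so it depends on the direction of each marker.

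**False-positive rates.** These come from 200,000 simulated trials per row with ρ = 0. The unadjusted test is Pearson's on N − 2 degrees of freedom. The adjusted test centres each variable within arm and uses N − 3.

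| Per arm | Arm effects | Unadjusted, .05 / .005 | Adjusted, .05 / .005 |
|---|---|---|---|
| 15 | 0.74 and 0 | 5.0% / 0.5% | 5.0% / 0.5% |
| 15 | 0.5 on both | 6.1% / 0.7% | 5.1% / 0.5% |
| 15 | 0.74 on both | 9.8% / 1.5% | 5.0% / 0.5% |
| 15 | 1.0 on both | 19.0% / 3.7% | 4.9% / 0.5% |
| 15 | 1.5 on both | 54% / 19.6% | 4.9% / 0.5% |
| 10 | 0.74 on both | 7.9% / 1.0% | 5.0% / 0.5% |

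**When a true association exists.** Take ρ = 0.3 and 15 per arm. With arm effects of 0.74 in the same direction, the formula gives (0.3 + 0.1369) / 1.1369 = 0.38, and the simulated mean is 0.38. With arm effects of opposite sign it gives (0.3 − 0.1369) / 1.1369 = 0.14, and the simulated mean is 0.13. The adjusted estimate averages 0.29 to 0.30 in both cases. Leaving arm out can therefore inflate a real link or hide it.

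**Cost of adjustment.** The critical |r| is t / √(t² + df). At N = 30 it moves from 0.361 (28 df) to 0.367 (27 df) at .05, and from 0.499 to 0.507 at .005.

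**The case against.** The strongest reply is that the documents never say the arms are combined. They are silent, and within-arm or adjusted correlations are not excluded. That stands: combining the arms is an inference from the absence of an arm term, helped by the fact that the authors name condition or group in the ANOVAs and t-tests. If a within-arm analysis is intended, the same sentence is still needed to say so.

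A second reply is that the distortion is modest. It needs an arm effect on both variables. At 0.5 it barely shows, and at 0.74 it adds about five percentage points at .05 and one at .005. This also stands. The 19% and 54% figures rest on arm effects that the documents do not support.

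A third reply is that 15.2 makes feasibility the main goal and admits that power is uncertain, while the ANOVAs would show whether both group means had moved. This limits the consequence but does not remove it. Section 15.3 still attaches significance thresholds, and a reader of the ANOVAs could not separate the two components of a reported r.

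A reader might also infer that the analysis fails whenever the trial's hypotheses hold. It does not. Aim 4 predicts a real association, and if one exists in the same direction as the product of the arm effects, an unadjusted correlation overstates it without inventing it.

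**Conclusion.** The concern holds in a limited form, and the plan should be changed. As written, sections 15.1 and 15.3 leave arm out of the correlations that serve Aim 4, while Aims 3 and 4 predict the condition under which leaving it out causes bias. At the only effect size in the documents, applied to both variables by assumption, the false-positive rate roughly doubles at .05 and triples at .005. The stricter imaging threshold lowers the absolute rate but does not remove the bias. The documents do not say which threshold applies to the EEG and ECG measures, so both columns are relevant.

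Three stronger readings are tempting and not supported:
- That the spurious correlation is always positive. Aim 4 expects some markers to rise and others to fall, so the sign varies.
- That a within-person link is at issue. Each participant gives one change score per variable, so the quantity is an association between participants within an arm.
- That Aim 4 will report a false mechanism. This depends on arm effects that nobody yet knows.

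**What to change.** In 15.1 and 15.3, state that associations between change scores will be estimated as partial correlations adjusted for randomised arm, or equivalently by regression with an arm term. Show the arm-specific estimates with confidence intervals beside them, as description only, and label the whole set exploratory.

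The cost is one sentence in each section and one degree of freedom per analysis, with no new data. No other covariate is needed to repair this defect. Adding a baseline score would be a separate choice and would use a further degree of freedom.
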